1. BACKGROUND AND JUSTIFICATION

1.1 Mobile Fluoroscopy and Vascular Procedures

Over the past 25 years, fluoroscopically guided interventional procedures have rapidly increased worldwide.^{2, 3} Fluoroscopy guidance provides surgeons and interventional specialists with the improved ability to assess anatomy and implant materials, ⁴ as well as guide catheters, guidewires, and stents through small vessels and pathways throughout the human body.²

In modern angiography, fluoroscopy provides necessary imaging guidance during dynamic vascular procedures, such as aortic aneurysm repairs, percutaneous artery angioplasty, and angiographic examinations. ⁵ Preoperative fluoroscopy may also be necessary for arteriography of the aorta and other vessels to determine precise anatomical relations when the proximal landing zone of a stent graft cannot be determined by non-invasive imaging. ⁶ Furthermore, peripheral angiography is regarded as the most accurate imaging tool for definitive diagnostics and preoperative planning of surgical and endovascular interventions in patients with advanced arterial disease.⁷

Gastrointestinal imaging has significantly evolved since the 1950s and fluoroscopy maintains a critical role in GI radiology. Mobile fluoroscopy is accepted as safe and effective for use during intraoperative cholangiography and external percutaneous biliary drainage procedures, and fluoroscopic imaging of upper gastrointestinal series has demonstrated better tumor localization when compared to endoscopic examination.

In contemporary clinical practice, complicated urologic procedures, including endourologic procedures such as retrograde cholangiopancreatography and upper urinary tract procedures are increasingly being performed using mobile C-arm fluoroscopy. With the advent of more complex fluoroscopically guided procedures, new interventional techniques and devices, such as the device under investigation in this study, are being developed and introduced to the market.

This prospective clinical study is being conducted to acquire image guidance adequacy data from physicians conducting clinically-indicated vascular, gastrointestinal (GI), urology and pain management procedures for engineering use, as deemed appropriate by the Sponsor, for the investigational OEC Elite™ CFD Mobile Fluoroscopy System –Motorized Configuration (OEC Elite) in the vascular configuration. Clinical procedures included in this study will involve three (3) anatomical regions of interest – extremities and neck, thorax, and abdomen and pelvis. These regions are being targeted because they represent the range of clinical applications and anatomical regions intended for OEC Elite in the vascular configuration.

1.2 Pre-Clinical Trials and Previous Clinical (human) Experience

GE Healthcare (GEHC), the study Sponsor, is a manufacturer of mobile fluoroscopy equipment and has extensive experience in conducting clinical trials.

A GEHC-sponsored study of human cadaveric tissue was conducted as part of feasibility and optimization of the investigational device's predicate, the OEC 9900 Elite (Study Title: A Diagnostic Capability Bench Study of An SSXI Mobile Fluoroscopy System and the OEC® 9900 Elite Mobile Fluoroscopy System; GEHC Study Number: 104-2014-GES-0003). A preclinical study using the swine animal model was recently conducted by the Sponsor for software optimization of the vascular configuration prior to implementing investigational OEC Elite in the vascular configuration in the clinical setting (Study Title: A Preclinical Imaging Study of the OEC Elite Vascular System; GEHC Study Number 104-GES-2016-0001).

In addition, the Sponsor has conducted research on previous non-motorized CFD (flat panel detector) systems. Imaging Evaluation of the OEC Elite Mobile Fluoroscopy System (GEHC Study Number 104-GES-2015-0003) was conducted to gather image data for a regulatory submission on the OEC Elite CFD. Two other studies, Clinical Evaluation of the OEC Elite Vascular Mobile Fluoroscopy System (GEHC Study Number 104-2016-PTHS-0005) and Evaluation of the OEC Elite Vascular Mobile Fluoroscopy System (GEHC Study Number 104-2017-GES-0001) were conducted to gather workflow and survey data.

1.3 Controls and Minimization of Bias

All reasonable attempts will be made to control and minimize bias during this study, including the following:

- Subjects will be consecutively enrolled from the patients screened until the accrual quota is filled, with the intent of limiting selection bias;
- Spectrum bias will be limited by using a population expected to be representative of the general population at the investigational site, without regard to race or ethnicity.

2. DEVICE/PRODUCT DESCRIPTION

2.1 Identity, Mechanism, and Function

Name: OEC Elite™ CFD Mobile Fluoroscopy System--Motorized Configuration

Modality/Type: Surgery

Manufacturer: GE OEC Medical Systems, Salt Lake City, UT, USA

Software version: The most current version available will be used.

Regulatory Status: Pre-market

Note: A record of number of devices issued, along with applicable identification numbers (e.g. serial/lot/batch) and components/accessories used in this study will be retained by the Sponsor as part of the clinical history file (CHF), as required by applicable laws and regulations.

The OEC Elite[™] CFD Mobile Fluoroscopy System--Motorized Configuration (OEC Elite) is a medical device centrally comprised of a mobile C-arm with flat-panel detector and a mobile workstation that displays resultant images. The device includes hardware and software capable of generating and receiving x-ray signals to produce images of bone and living tissues, and a mobile workstation that includes image display and user interface. As with the predicate device, the investigational device is motorized and uses a tableside Remote User Interface (RUI) to enable the operator to move the C-arm without touching it. The central difference between the predicate OEC 9900 Elite MD device and the investigational system is the replacement of an image intensifier detector with a flat-panel detector.

For this study, the OEC Elite (Figure 1) will be provided to the investigational site in the VAS MTS configuration with a 31-cm flat panel detector.

Figure 1 – Investigational OEC Elite Mobile Fluoroscopy System

The research device, instructions for use, or packaging shall indicate that the research device is for use in a research investigation, in accordance with applicable regulations in Canada per Medical Device Regulations (SOR/98-282), Part 3, Sections 79-88 and other applicable laws and regulations.

The investigational device will be exclusively used for research procedures and only as set forth in an Ethics Committee (EC) approved study protocol, in accordance with applicable laws and regulations.

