2.4.1 Issuance

The Sponsor will provide the site with devices, including necessary hardware and software components of the device. The Sponsor will provide necessary maintenance for the investigational device(s) installed at the sites. GE technical support will be available, as needed, to maintain integrity of study data.

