3.2 Study Endpoints

3.2.1 Primary Endpoints:

The primary endpoint is the per-subject investigator report of imaging guidance adequacy to complete the procedure (Y/N).

3.2.2 Secondary Endpoints:

The secondary endpoints are the total number of surveys reflecting the investigator opinion of procedures performed and the image data collected.

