5.4 Malfunction/Error Handling

The site should report the occurrence and resolution of any procedures terminated due to non-recoverable malfunctions (i.e. malfunctions or errors with OEC Elite that prevent image collection and are not able to be immediately resolved by the device operator). The site should also report recoverable errors (i.e. issues with the device that do not prevent image collection and are able to be resolved immediately by the device operator) and operator errors. The occurrence of any recoverable error, operator error, or non-recoverable malfunction will be reported on the subject's CRF.

In uncommon cases, the research procedures using the investigational device may need to be terminated unexpectedly. If the investigator suspects that a subject would be at increased risk, or that the subject's clinical procedure will not be able to be completed using the investigational device in this study, the investigator may terminate the procedure at any time and for any reason. In some cases, it may not be feasible to end a procedure; in which case, equivalent, site-provided commercial fluoroscopy equipment (such as the predicate device or equivalent) may be used. The site will ensure that access to alternative commercial fluoroscopy equipment is maintained during all procedures. All patient care and management

decisions for terminated procedures will be made outside of this study according to the sites' standard clinical practices and the subject's regular physician's or investigator's medical judgment.

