7.3 Case Report Form

The study procedure CRF will report the following:

- Basic demographic
- Type of procedure or technique being performed
- Anatomical region being imaged
- Contrast information

- User Evaluation Survey
- Guidance Adequacy

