9.3 Management of Protocol Modifications and Amendments

Substantial amendments will only be implemented after EC approval.

A deviation is any instance(s) of failure to follow, intentionally or unintentionally, the requirements of the protocol. Under emergency circumstances, deviations from the protocol to protect the rights, safety, and wellbeing of human subjects may proceed without prior approval of the Sponsor and the EC/CA. Such deviations shall be documented and reported to the Sponsor and the EC as soon as possible. Deviations will be reported as:

- **Critical Deviations:** Deviations that significantly affect the safety, efficacy, integrity, or conduct of the study. These deviations must be reported to the Sponsor no later than 5 working days from awareness of occurrence and reported to the EC per the deviation reporting policy.
- **Non-Critical Deviations:** Protocol deviations that do not significantly affect the safety, efficacy, integrity, or conduct of the trial. These deviations must be documented on the CRF Protocol Deviation page and will be reviewed by the study monitor.

Non-substantial modifications may be made during the normal course of device optimization, maintenance, and feasibility testing. Non-substantial modifications will be communicated to the CA as soon as possible, if applicable, and to the EC per their policy.

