11.1.2 Data Handling and Record Keeping

All documents and data shall be produced and maintained in a manner that assures control and traceability.

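### Does the absence of a required software-version record for each procedure undermine the adequacy, survey and error data?

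*Combined protocol and SAP*

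**What the plan says.** On the software itself, Section 2.1 states: "Software version: The most current version available will be used". It names no number and does not say whether the version is settled at installation or follows later releases. Section 2.4.1 puts supply with the sponsor: "The Sponsor will provide the site with devices, including necessary hardware and software components of the device". The same section has the sponsor maintain the installed device.

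On change during the study, Section 9.3 states: "Non-substantial modifications may be made during the normal course of device optimization, maintenance, and feasibility testing". These changes are to be notified to the competent authority where applicable, and to the ethics committee under its own policy.

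On records, Section 2.1 has the sponsor keep in its clinical history file "A record of number of devices issued, along with applicable identification numbers (e.g. serial/lot/batch) and components/accessories used in this study". Section 2.4 asks for accurate and adequate device records from shipment until return or disposal. Section 7.3 lists what the procedure CRF reports: demographics, procedure type, region, contrast, survey and guidance adequacy. Software version is not on that list. Section 5.4 adds that "The occurrence of any recoverable error, operator error, or non-recoverable malfunction will be reported on" the subject's CRF. Section 11.1.2 sets the general standard: "All documents and data shall be produced and maintained in a manner that assures control and traceability".

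The primary endpoint in Section 3.2.1 is a yes/no report of guidance adequacy for each subject.

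**The concern.** Software is part of what produces the image in this system. Section 1.2 mentions a preclinical study run to optimise the software of the vascular configuration, so the sponsor itself treats software as relevant to performance. Adequacy and errors are recorded per subject, whereas the required device records are at device level, and a serial number would not be expected to change when software is updated.

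If a new build were installed partway through, the listed CRF items would not show which build lay behind a negative adequacy report, a critical survey answer or an error. Nor would they show how many subjects were imaged on the last build. Section 1.1 says the adequacy data are for engineering use, and Section 10.2 expects enough procedures to demonstrate clinical performance. Data that mix builds without labels would serve both purposes less well.

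**Working it through.** The plan has no figure to reproduce: Section 10.2 gives no formula for the sample size, Section 10.1 states no hypothesis and Section 10.3 plans no analysis. The check is therefore mainly a reading of the relevant sections side by side.

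1. **Will the version change?** The sentence in Section 2.1 can mean the version current at installation or a rolling one. Section 9.3 permits modifications but does not mention software updates or say that any will occur. A change is possible, not planned.

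2. **Is the CRF list in Section 7.3 complete?** No. Section 5.4 places device errors on the subject's CRF, Section 4.7 a final evaluation at withdrawal, and Section 9.3 a protocol deviation page. None of these is on the Section 7.3 list. An item missing from that list is weak evidence that it will not be collected.

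3. **Could a version be matched to a procedure from records already required?**
 - Section 2.1 requires a record of components used, and Section 2.4.1 counts software among the device's components. Read together, software can fall within the clinical history file record.
 - Section 2.4 requires adequate device records throughout the time the device is at the site.
 - Section 9.3 requires modifications to be notified as described above, which should leave a record of the change.
 - Section 11.1.3 requires each subject's source documents to be kept. These can be expected to carry the procedure date.
 - Section 4.1 limits the study to one site.

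 The dates of any change, set against procedure dates at a single site, would give the version for each subject.

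4. **What about errors and negative adequacy reports?** Section 8.5 requires device deficiencies to be investigated and documented. Section 8.2 defines them to include malfunctions, use errors and inadequate performance. An error, or a negative report caused by poor imaging, would normally enter that process, where the build is an obvious thing to establish. Survey remarks short of a deficiency would rely on the date matching in step 3.

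5. **Does any result change?** Suppose all 40 subjects (the maximum in Section 4.3) are reported adequate. The exact two-sided 95% lower limit when all n are adequate is 0.025^(1/n):
 - n = 40: 0.025^(1/40) = 91.2%
 - n = 20: 0.025^(1/20) = 83.2%, if an update fell midway (an assumption; the documents give no date)

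 The second limit is lower because fewer subjects used each build, and a version field would not alter that. The overall count of 40 of 40 is the same either way. The plan does not define adequacy on a particular build as a quantity to be estimated, so neither limit measures a fault in it.

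**The case for a change.** The strongest case for a change is that reconstruction is possible but not assured. No section requires a dated log of software changes, Section 7.3 lists neither a procedure date nor a device identifier, and Section 11.1.2 sets a principle without a mechanism. One CRF item written at the time of the procedure would be more dependable than matching dates later, would cost almost nothing, and would show that a single build was used if that was so.

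A mixture could also hide a difference. Under assumed counts, 36 of 40 adequate (90%) is what one would see with 20 of 20 on one build and 16 of 20 (80%) on the other, since 20 + 16 = 36. Without the version these cannot be told apart from an even spread of the four negative reports.

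It stands that no section expressly asks for the version per procedure, and that recording it is good practice. It does not stand that the reports could not be attributed: that reads each record provision alone and leaves out Sections 2.4, 8.5 and 11.1.3. The masking example needs an update, a split and four negative reports, none of which the documents supply.

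**Conclusion.** No change to the plan is needed. This is missing operational detail that those running the study can fill sensibly. The party that wants the data for engineering use also supplies the software, maintains the device, controls any update and keeps the clinical history file. It can be expected to know which build was installed and when.

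The stated objectives in Section 3.1 are to collect feedback on guidance adequacy, images and survey responses. All of these are met whether or not the version appears on the CRF. With no hypothesis and no planned analysis, error rates and power are not in play, and the overall adequacy count does not move.

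The size is nil if one build serves every subject. If an update is assumed, the effect is limited to how readily individual reports can be assigned to a build. This conclusion rests on two assumptions: that the sponsor's device and modification records are dated, and that source documents show the procedure date. Both are ordinary, but neither is spelled out in the protocol. If more than one version is in fact used, saying so in the final report is normal practice and needs no amendment.

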2.2 Intended Use

The OEC Elite Mobile Fluoroscopy System is designed to provide fluoroscopic and digital spot images of adult and pediatric populations during diagnostic, interventional, and surgical procedures. Examples of a clinical application may include: orthopedic, gastrointestinal, endoscopic, urologic, neurologic, vascular, critical care, and emergency procedures.

This study will include vascular, gastrointestinal (GI), urology and pain management procedures in an adult population. Study procedures will be conducted in accordance with the site's standard of care.

2.3 Concomitant/Ancillary Administrations

2.3.1 Medications and Biologic Products

No medications or biologic products will be administered as part of study procedures.

2.3.2 Laboratory Tests and Sample Processing

No laboratory tests or sample processing is planned as part of the study procedures.

2.4 Accountability

Accurate and adequate records will be maintained for all devices, from time of shipment to the site until return or disposal of all devices issued by the Sponsor as part of this study, as required by applicable

laws and regulations. The Principal Investigator will be ultimately responsible for the security and integrity of research devices at the investigational site during the study.

2.4.1 Issuance

The Sponsor will provide the site with devices, including necessary hardware and software components of the device. The Sponsor will provide necessary maintenance for the investigational device(s) installed at the sites. GE technical support will be available, as needed, to maintain integrity of study data.

2.4.2 Disposition

Upon completion of the study, Sponsor-provided devices at the investigational site will be de-installed by Sponsor-authorized engineers and returned to the Sponsor, or otherwise dispositioned, in accordance with applicable laws and regulations. Identifiable subject information will be removed from the device(s) prior to dispositioning devices.

2.5 Anticipated Risks and Benefits

The device under study has undergone risk assessment, in accordance with International Standards Organization (ISO) 14971:2012, and risks have been mitigated to levels as low as reasonably practicable (ALARP).

The investigational OEC Elite is expected to present similar potential risks to patients, operators, or others in this study as the predicate commercial device, OEC 9900 Elite, when used under similar clinical indications for use. The risks of study participation are not expected to be different than those of non-study procedures. Because basic image guided fluoroscopy will be used for conventional procedure applications, there will be no post-trial care or follow-up required by this study.

As with all x-ray devices, OEC Elite uses the minimum possible ionizing x-ray radiation dose, which is within acceptable limits set forth by applicable local laws and regulations necessary to complete a procedure. Because the radiation dose and procedural duration widely vary for the procedures included in this study, there is no prospective per-procedure maximum radiation dose or duration prescribed by this protocol. All procedures will be conducted per the clinical standards of the site and the medical discretion of physicians performing the clinically indicated study procedures.

In the unlikely event that a device error prevents or impairs image acquisition, it is possible that a subject may require alternative or additional imaging to complete an intervention or exam. If imaging is not adequate or diagnostic-quality images cannot be obtained using the investigational device, the subject will not undergo additional investigational imaging. Necessary medical care will be provided by the sites, and equivalent, site-provided commercial fluoroscopy systems (e.g. the predicate device or equivalent) will be readily available throughout the study.

Subjects who undergo additional or elongated imaging procedures may be at a small increased risk because of additional x-ray exposure and possible additional procedure time, which may also impact the duration and/or dosages of anesthesia and contrast administration.

Subjects are not expected to benefit directly from study participation; however, the results may benefit future patients by helping to better understand the device under study.

2.5.1 Risk Category and Rationale

In Canada, the OEC Elite[™] CFD Mobile Fluoroscopy System—Motorized Configuration is a Class III medical device, as defined by Schedule 1, Part 1, Rule 8 of the Medical Devices Regulations (SOR/98-

282). Use of OEC Elite is not expected to pose significant risk to human subjects in accordance with the standards of Health Canada's Medical Device Regulations, Part 3 – Medical Devices for Investigational Testing Involving Human Subjects (SOR/98-282, §79-88).

3. PURPOSE OF THE STUDY

The purpose of the study is to collect survey data on the use of the OEC Elite based on the routine clinical use of the device.

3.1 Study Objectives:

3.1.1 Primary Objective:

The primary objective is to collect investigator feedback on imaging guidance adequacy of the OEC Elite during clinical procedures.

3.1.2 Secondary Objective(s):

The secondary objectives of this study are to collect image data acquired during clinical procedures and to collect investigator feedback via surveys on the use of the system during clinical procedures.

